13.3.7 BLINK RATE

Blink rate will be recorded at Visit 2 (Day 1), Visit 3 (Day 8), Visit 4 (Day 15), and Visit 5 (Day 29) at pre-CAE®. Analyses will only be produced for study eye.

Visit-based data will be summarized using continuous descriptive statistics by treatment group. Change from baseline will also be summarized with continuous descriptive statistics.

Two-sample t-tests will be used to analyze differences between treatment groups at each visit between active treatment and vehicle. The differences in means, two-sided 95% CIs for the difference in means, and two-sided p-values will be reported.

Change from baseline will be analyzed using an ANCOVA model with adjustment for baseline blink rate and site, and treatment group as the explanatory variable. The LS means, LS mean differences, SEs, two-sided 95% CIs for LS means, two-sided 95% CIs for the difference in means, and two-sided p-values will be reported from the ANCOVA model. Two-sample t-tests will be used as sensitivity analysis. The mean differences, SEs, two-sided 95% CIs for the difference in means, and two-sided p-values will be reported from the sensitivity analyses where applicable. Paired t-tests will be used to analyze change from baseline within each treatment group.

Analyses will use ITT population with control-based pattern mixture model imputation as described in section 13.1.1. The random number seeds for the monotone imputation and pattern mixture model imputation will be SEED = 6754416 and SEED = 234123, respectively.

A subject level listing of blink rate will also be produced.

13.3.8 OCULAR DISCOMFORT SCALE (ORA CALIBRA®)

Ocular discomfort scores will be subjectively graded by the subjects using the Ora Calibra® Ocular Discomfort Scale at all visits at pre-CAE® and post-CAE®. The Ocular Discomfort Scale ranges from 0 to 4 where 0 = No Discomfort, 1 = Intermittent Awareness, 2 = Constant Awareness, 3 = Intermittent Discomfort, and 4 = Constant Discomfort. Analyses will only be produced for study eye.

Visit-based data will be summarized using continuous descriptive statistics for each symptom by treatment group at each time point (pre-CAE® and post-CAE®). Change from baseline will also be summarized with continuous descriptive statistics.

Two-sample t-tests will be used to analyze differences between treatment groups at each visit between active treatment and vehicle. The differences in means, two-sided 95% CIs for the difference in means, and two-sided p-values will be reported.

Change from baseline will be analyzed using ANCOVA adjusted for baseline discomfort score and site, and treatment group as the explanatory variable. The LS means, LS mean differences, SEs, two-sided 95% CIs for LS means, two-sided 95% CIs for the difference in means, and two-sided p-values will be reported from the ANCOVA model. Two-sample t-tests will be used as sensitivity analysis. Paired t-tests will be used to analyze change from baseline within each treatment group.

Analyses will use ITT population with control-based pattern mixture model imputation as described in section 13.1.1. The random number seeds for the monotone imputation and pattern mixture model imputation will be SEED = 8675478 and SEED = 523426, respectively.

A subject-level listing of ocular discomfort scores will also be produced.

13.3.8.1 OCULAR DISCOMFORT SCALE (ORA CALIBRA®) DURING CAE®

Ocular discomfort scores will be assessed every 5 minutes during the CAE® exposure at Visit 1 (Day -14), Visit 2 (Day 1), Visit 4 (Day 15), and Visit 5 (Day 29). Assessments at 0 minutes, 90 minutes, change from 0 to 90 minutes, change from 0 to last timepoint and changes from baseline will be summarized by treatment group, visit, and timepoint using continuous descriptive statistics, including two-sided 95% CIs. Last timepoint is described as last recorded discomfort score within a CAE® exposure.

For the ocular discomfort score at 0 minutes, at 90 minutes, change from 0 to 90 minutes, and change from 0 to last time point, two-sample t-tests will be employed to compare treatment and Vehicle means at each post-baseline visit and time point. The differences in means, two-sided 95% CIs for the difference in means, and p-values will be reported.

Changes from baseline will be compared between treatment groups using ANCOVA models that adjust for baseline and site. The LS means, LS mean differences, SEs, two-sided 95% CIs for the difference in means, and two-sided p-values will be reported. Two sample t-tests will also be conducted. Within each treatment group, paired t-tests will be conducted to compare change from baseline.

LS means from the ANCOVA will be displayed graphically in a line graph with standard error bars by treatment group.

Analyses will use ITT population with control-based pattern mixture model imputation as described in section 13.1.1. The random number seeds for the monotone imputation and pattern mixture model imputation will be SEED = 728436 and SEED = 543685, respectively.

A subject listing of ocular discomfort scores during CAE® will be provided.

13.3.8.2 OCULAR DISCOMFORT SCALE (ORA CALIBRA®) DURING CAE® MIXED MODEL REPEATED MEASURES

Ocular discomfort scores will be assessed every 5 minutes during the CAE® exposure at Visit 1 (Day -14), Visit 2 (Day 1), Visit 4 (Day 15), and Visit 5 (Day 29). Assessments at 0 minutes, 90 minutes, change from

0 to 90 minutes and changes from baseline will be summarized by treatment group, visit, and timepoint using continuous descriptive statistics, including two-sided 95% CIs.

Change from baseline will be assessed using a mixed-effect model for repeated measures (MMRM) to compare active treatment and vehicle at Visit 4 (Day 15), and Visit 5 (Day 29) while accounting for the correlations among the repeated measurements during the CAE®. The model will include treatment group; time (nominal time will be used); treatment by time interaction, and timepoint matched baseline ocular discomfort score as fixed effects; and subject as the random effect. The following SAS® code will be used:

```
PROC MIXED DATA = INDATA METHOD=REML;
  CLASS SUBJID TREATMENT TIME SITE;
  MODEL CHG_ODS = ODS_BASE SITE TREATMENT | TIME
    / SOLUTION COVB DDFM=KR;
  REPEATED TIME / TYPE = UN SUBJECT = SUBJID;
  LSMEANS TREATMENT TREATMENT*TIME/ CL PDIFF;
  ODS OUTPUT LSMEANS = OUTLS DIFFS = OUTDIFFS;
RUN;
```

where

- *SUBJID* is the subject ID
- *SITE* is the Site ID
- *TREATMENT* is the name of the treatment group variable
- *TIME* is the nominal time of the measurement
- *CHG_ODS* is the change from baseline ocular discomfort score
- *ODS_BASE* is the timepoint matched baseline ocular discomfort score in the study eye
- *OUTLS* is the name of the output dataset that contains the statistical results for the treatment means from the MMRM
- *OUTDIFFS* is the name of the output dataset that contains the statistical results for the differences in treatment means from the MMRM

If the MMRM does not converge with an unstructured (TYPE = UN) covariance matrix, Toeplitz (TYPE = TOEP) and compound symmetry (TYPE = CS) structures will be utilized in order until convergence is achieved. If the MMRM with compound symmetry does not converge, MMRM statistical inferences will be represented as not calculable.

The LS means, LS mean differences, SEs, two-sided 95% CIs for the difference in means, and two-sided p-values will be reported from the MMRM.

Analyses will use ITT population with observed data only.

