10.4.5 Efficacy Analyses

Primary Efficacy Analyses

The primary comparisons of change from baseline in post-CAE inferior corneal staining and ocular discomfort between the [REDACTED] K-161 [REDACTED] group and the vehicle group at Day 29, will be performed using analysis of covariance (ANCOVA) models. The respective baseline post-CAE score will be included as a covariate in each model and site will be included as a fixed effect. Treatment by baseline and treatment by site interactions will be explored in separate models and, if significant, analyses will be performed by baseline stratification and/or site, respectively, to further examine significant interactions. The primary analyses will use the ITT population.

For the primary endpoints, multiple imputation with MCMC techniques will be used. Imputation will be performed by treatment arm with imputation terms for baseline and Day 29 scores.

Secondary Efficacy Analyses

Secondary and exploratory endpoints will be analyzed similarly to the primary analyses on the ITT population. Continuous and ordinal variables collected at each visit will be summarized descriptively (n, mean, standard deviation, median, minimum and maximum), and analyzed with ANCOVA models comparing each K-161 group to the vehicle group. All visit-based data will be analyzed by visit and for each timepoint, if applicable, as well as the change from baseline.

Data collected pre- and post-CAE will also be analyzed for the change from pre- to post-CAE within each visit. Data collected during the CAE will also be analyzed using repeated measures models including all of the time points from a CAE exposure.

For the two important secondary endpoints, other secondary, and exploratory endpoints, multiple imputation with MCMC techniques will be used. Imputation will be performed by treatment arm with imputation terms for baseline and Day 29 scores.

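### If the unstructured matrix fails in the exploratory during-CAE MMRM, both fallbacks force one variance on all time points, which can distort the per-time standard errors

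*SAP*

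**What the plan says.** SAP 13.3.8.2 plans a mixed model for change from baseline in ODS during the CAE exposure, comparing active treatment with vehicle at Visit 4 and Visit 5 on observed data in the ITT population.

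- **Text.** Arm, nominal time and their interaction are listed first; the list then closes with "timepoint matched baseline ocular discomfort score as fixed effects; and subject as the random effect". Site is not named.
- **Code, which the section says will be used.** The fixed effects are "MODEL CHG_ODS = ODS_BASE SITE TREATMENT | TIME" and the covariance is "REPEATED TIME / TYPE = UN SUBJECT = SUBJID". There is no RANDOM statement, visit effect or BY statement. TIME "is the nominal time of the measurement".
- **Fallback.** If the unstructured fit does not converge, "Toeplitz (TYPE = TOEP) and compound symmetry (TYPE = CS) structures will be utilized in order until convergence is achieved". If compound symmetry also fails, no inference is reported.

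Protocol 10.4.5 describes the same analysis: "Data collected during the CAE will also be analyzed using repeated measures models including all of the time points from a CAE exposure". SAP 8.5 places everything outside the four hierarchical tests in the exploratory category.

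**The concern.** Scores at 0, 5, ..., 90 minutes give 19 time points and 190 unstructured covariance parameters, estimated from a coarse integer score. Neighbouring scores are likely to be highly correlated. SAP 13.3.8.1 also foresees exposures that end early, since it defines a last recorded score within an exposure. A fallback is therefore a real possibility.

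The two structures named both hold the variance constant across the exposure. The CAE is a stress test, and the spread of change scores could widen as discomfort builds or narrow as scores approach the ceiling of 4. A common variance would then give intervals that are too narrow at some time points and too wide at others. The section reports treatment-by-time least squares means and differences, so the error would reach the tables.

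Two loose ends in the section add to this. Text and code describe different models, and nothing states how the two visits enter the fit.

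**Working it through.** **1. The plan's own figure on this scale.** SAP section 5 gives 60 per group, difference 0.49, SD 0.82 and two-sided 0.05, with about 90% power. The standard error is 0.82 × √(2/60) = 0.1497, and 0.49/0.1497 = 3.27. Power is Φ(3.27 − 1.96) = 0.905 by the normal approximation and 0.901 by the noncentral t. The figure reproduces. No power figure is given for the MMRM.

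**2. Parameter counts.** The number of time points is m = 90/5 + 1 = 19.

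| Structure | Formula | Parameters | Variance by time |
|---|---|---|---|
| Unstructured | 19 × 20/2 | 190 | free |
| TOEPH | 19 + 18 | 37 | free |
| CSH | 19 + 1 | 20 | free |
| TOEP | m | 19 | one common value |
| CS | 2 | 2 | one common value |

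**3. Standard error under a common variance.** With complete data the fitted common variance is the average of the variances over time. Let r be the 0-minute SD divided by the 90-minute SD, and let variance run linearly in time. Reported over true standard error at 90 minutes is √((r² + 1)/2), and the two-sided error rate is 2 × (1 − Φ(1.96 × ratio)).

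- r = 1: ratio 1.00, error 5.0%.
- r = 0.75: √(1.5625/2) = 0.884, error 8.3%.
- r = 0.5: √(1.25/2) = 0.791, error 12.1%.
- r = 1.25 (spread falls over the exposure): √(2.5625/2) = 1.13, so the standard error is about 13% too large.

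At 0 minutes the ratio is the same quantity divided by r: 0.884/0.75 = 1.18 and 0.791/0.5 = 1.58, so those intervals are too wide.

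On the ODS scale, take the planned 0.82 as the 90-minute SD and ignore covariate adjustment. The correct 95% half-width is 1.96 × 0.1497 = 0.293. Reported values would be 0.884 × 0.293 = 0.259 (r = 0.75) or 0.791 × 0.293 = 0.232 (r = 0.5).

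**4. Simulation check.** With four arms of 60, 4,000 runs and the SD (rather than the variance) linear from 0.50 to 0.82, the formula gives a 90-minute ratio of 0.814 and error of 11.1%. Simulated error was 9.8% at 90 minutes, 1.1% at 0 minutes, and 4.5% for the treatment effect averaged over time. The last figure is expected: in complete data compound symmetry reproduces the average variance and the average covariance, and so the variance of a time average. With constant SD the three error rates were 5.0% (0 minutes), 4.5% (90 minutes) and 5.2% (time-averaged).

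**5. Text against code.** A random subject intercept with independent residuals is compound symmetry with non-negative correlation: two parameters, and the structure the same section keeps as its last resort. The code has 190 parameters and a site effect.

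**6. Visit.** If Visits 4 and 5 were both in the input data, each subject would have two rows at every TIME level. The 38 × 38 within-subject block would have rank 19, and so be singular, under UN, TOEP and CS alike. Fitted one visit at a time, the problem does not arise.

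**The case against.** The strongest reply is that the error rates need two things together, neither of them shown: the unstructured fit must fail, and the variance must change materially over the exposure. Roughly 240 subjects for 190 parameters is not failure in itself. In a simulation of 240 complete exposures with rounded 0 to 4 scores, the covariance of the change scores was positive definite in 600 of 600 runs. That stands, although it does not test exposures that end early. The change score can also run from −4 to +4, so it has nine possible values, not five.

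A reader might make three stronger inferences, which the documents do not support.

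- **That the analysis as coded yields no result.** This requires the two exposures to be stacked. Nothing instructs that, and Protocol 10.4.5 speaks of the time points of a single exposure. Stacking would also fail visibly.
- **That the results will come from the random-subject model without site.** The code is what the SAP says will be used, and site is a fixed effect in the SAP's other change-from-baseline models. The text is plausibly loose wording for within-subject correlation.
- **That the during-CAE evidence depends on this model.** SAP 13.3.8.1 analyses the same scores with t-tests and with ANCOVA adjusted for baseline and site, including 90 minutes, and none of these relies on the MMRM covariance.

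What survives is that the fallback order excludes structures that are feasible and safer, and that the text and the handling of visits should be stated correctly.

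**Conclusion.** The point holds in limited form and is one to consider. If the unstructured matrix fails and the SD of ODS change varies over the exposure, the planned fallbacks misstate the precision of the per-time contrasts. Under the assumed ratios of 0.75 and 0.5, the 90-minute standard error is about 12% and 21% too small, and two-sided error is 8.3% and 12.1%. With near-constant SD the error is negligible, and the time-averaged contrast keeps about its nominal size in either case. The figures assume complete data and variance linear in time. The documents give no SD by time point, so the size of the effect in this trial is unknown. Because the analysis is exploratory, the primary conclusions and the study-wise alpha are not affected. The mismatch between text and code and the unstated visit handling are clarifications, and would not justify the point on their own.

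**What to change.** In SAP 13.3.8.2, before unmasking:

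1. Set the covariance order to UN, then TOEPH, then CSH, then TOEP, then CS. The heterogeneous structures need 37 and 20 parameters and leave the variance free at each time point.
2. Make the text match the code: add site as a fixed effect and delete the reference to subject as a random effect.
3. Add `BY VISIT;` to the code and say that each CAE exposure is modelled separately, as Protocol 10.4.5 implies. Crossing visit with time instead would need 38 × 39/2 = 741 unstructured parameters.

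The cost is a few words of SAP text, small code edits and, at worst, one or two extra fallback runs. No data collection or sample size changes.

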13.3.9 OCULAR DISCOMFORT & 4-SYMPTOM QUESTIONNAIRE (ORA CALIBRA® SCALE)

Subjects will rate the severity of each of the following symptoms (for both eyes [OU]) with regard to how both their eyes feel in general: overall ocular discomfort, burning, dryness, grittiness, and stinging according to the following 6-point (0 to 5) scale where 0 = None and 5 = Worst. Questionnaires will be recorded at all visits at pre-CAE® and post-CAE®.

Visit-based data will be summarized using continuous descriptive statistics for each symptom by treatment group at each time point pre-CAE® and post-CAE®. Change from baseline will also be summarized with continuous descriptive statistics.

Two-sample t-tests will be used to analyze differences between treatment groups at each visit between active treatment and vehicle. The differences in means, two-sided 95% CIs for the difference in means, and two-sided p-values will be reported.

Change from baseline will be analyzed using ANCOVA adjusted for baseline symptom score and site, and treatment group as the explanatory variable. The LS means, LS mean differences, SEs, two-sided 95% CIs for LS means, two-sided 95% CIs for the difference in means, and two-sided p-values will be reported from the ANCOVA model. Two-sample t-tests will be used as sensitivity analysis. Paired t-tests will be used to analyze change from baseline within each treatment group.

Analyses will use ITT population with control-based pattern mixture model imputation as described in section 13.1.1. The random number seeds for the monotone imputation and pattern mixture model imputation will be SEED = 3658465 and SEED = 9631723, respectively.

A subject-level listing of symptom scores will also be produced.

13.3.10 VISUAL ANALOG SCALE

Ocular symptoms of the VAS will recorded at all visits at pre-CAE® and post-CAE®. Subject will be asked to subjectively rate ocular symptoms (OU) by placing a vertical mark on the horizontal line to indicate the level of discomfort. The length of the assessment line is 100 mm; a measure of 0 mm corresponds to "No Discomfort" and 100 mm corresponds to "Maximal Discomfort." The ocular symptoms used for analysis are Burning/Stinging, Itching, Foreign Body Sensation, Blurred Vision, Eye Dryness, Photophobia, and Pain.

Visit-based data will be summarized using continuous descriptive statistics for each symptom by treatment group for each time point (pre-CAE® and post-CAE®). Change from baseline will also be summarized with continuous descriptive statistics.

Two-sample t-tests will be used to analyze differences between treatment groups at each visit between active treatment and vehicle. The differences in means, two-sided 95% CIs for the difference in means, and two-sided p-values will be reported.

Change from baseline will be analyzed using ANCOVA adjusted for baseline ocular symptom score and site, and treatment group as the explanatory variable. The LS means, LS mean differences, SEs, two-sided

95% CIs for LS means, two-sided 95% CIs for the difference in means, and two-sided p-values will be reported from the ANCOVA. Two-sample t-tests will be used as sensitivity analysis. Paired t-tests will be used to analyze change from baseline within each treatment group.

Analyses will use ITT population with control-based pattern mixture model imputation as described in section 13.1.1. The random number seeds for the monotone imputation and pattern mixture model imputation will be SEED = 432467 and SEED = 9434382, respectively.

A subject-level listing of VAS will also be produced.

13.3.11 OCULAR SURFACE DISEASE INDEX

The OSDI[®] is assessed on a scale of 0 to 4, where 0 = None of the Time, 1 = Some of the Time, 2 = Half of the Time, 3 = Most of the Time, and 4 = All of the Time. The OSDI[®] asks the following 12 questions at the subject level:

Have you experienced any of the following during the last week?

1. Eyes that are sensitive to light?
2. Eyes that feel gritty?
3. Painful or sore eyes?
4. Blurred vision?
5. Poor vision?

Have problems with your eyes limited you in performing any of the following during the last week?

6. Reading?
7. Driving at night?
8. Working with a computer or bank machine (ATM)?
9. Watching TV?

Have your eyes felt uncomfortable in any of the following situations during the last week?

10. Windy conditions?
11. Places or areas with low humidity (very dry)?
12. Areas that are air conditioned?

The total OSDI[®] score is calculated by the following:

$$\text{OSDI}^{\circledast} = \frac{(\text{Sum of Scores}) \times 25}{\# \text{ of Questions Answered}}$$

Note that the number of questions answered in the denominator should exclude those questions with a response of "N/A."

Ocular Surface Disease Index[®] will be assessed at all visits at pre-CAE[®].

Visit-based data will be summarized using continuous descriptive statistics for each OSDI® subtotal score and total OSDI® score by treatment group. Change from baseline will also be summarized with continuous descriptive statistics.

Two-sample t-tests will be used to analyze differences between treatment groups at each visit between active treatment and vehicle. The differences in means, two-sided 95% CIs for the difference in means, and two-sided p-values will be reported.

Change from baseline will be analyzed using ANCOVA adjusted for baseline OSDI score and site, and treatment group as the explanatory variable. The LS means, LS mean differences, SEs, two-sided 95% CIs for LS means, two-sided 95% CIs for the difference in means, and two-sided p-values will be reported from the ANCOVA. Two-sample t-tests will be used as sensitivity analysis. Paired t-tests will be used to analyze change from baseline within each treatment group.

Analyses will use ITT population with control-based pattern mixture model imputation as described in section 13.1.1. The random number seeds for the monotone imputation and pattern mixture model imputation will be SEED = 354715 and SEED = 863267, respectively.

A subject-level listing of OSDI will also be produced.

14. [REDACTED]

14.1.1

14.1.2

14.1.3 [REDACTED]

14.1.4 EFFICACY ENDPOINTS THAT ARE COMPARED AGAINST [REDACTED] K-161 FOUR TIMES DAILY ([REDACTED] (I.E., [REDACTED)
K-161 TWICE DAILY [REDACTED] K-161 [REDACTED] AND VEHICLE [REDACTED]

These analyses will be conducted as described in section 13 with secondary endpoints.

15. Safety Analyses

All safety analyses will be conducted using the safety population.

